10.1.3.1 Sample Processing and Routing

Samples will be processed in ECOG-ACRIN's Leukemia Translational Studies Laboratory and sent to [name] laboratory as frozen viable cells or isolated DNA if viable cells are not available. [name] will perform his studies (Section [10.3](#)) and/or forward DNA to [name] for [name] studies (Section [10.4](#)). From the remaining specimen, an aliquot will be sent to GenPath for Array CGH studies.

The priority of work is as follows: 1. [name] 2. [name] 3. Array CGH at GenPath. In some cases, RNA may not be available for epigenetic studies ([name]), although DNA may be available for mutation analysis ([name]) and Array CGH (GenPath). Bone marrow and peripheral blood smears may be forwarded to [name] at Stanford University for morphology review.

[name] laboratory will perform the P-glycoprotein and CXCR4 expression studies as outlined in Section [10.5](#).

Rev. 8/13 10.2 Cytogenetic Review

The cytogenetic review will be performed at the Mayo Clinic Cytogenetic Laboratory.

10.2.1 Sample Submission Schedule and Preparation Guidelines

Karyotypes must be collected and submitted at the following time points:

- Enrollment/Baseline
- Time of Outcome Following Induction (Prior to Consolidation) [at time of response assessment or off-study, whichever occurs first]
- End of Consolidation (Prior to 2nd Randomization - Step 3)
- Relapse

NOTE: Karyotypes are required at all time points.

10.2.1.1 Karyotypes (MANDATORY AT ALL TIME POINTS)

Within 30 days of specimen collection at each time point, investigators must send the two (2) original karyotypes per clone, FISH results, institution's cytogenetic laboratory report, the Leukemia Cytogenetic Form (#365R) to the ECOG-ACRIN Cytogenetic Committee.

NOTE: If cytogenetic studies are not successful, submit the laboratory report and #365R form to [name] by either mail or fax.

Original karyotypes will be returned, upon written request, when the review and analysis are complete.

10.2.1.2 Shipping Guidelines

Log the shipment into the ECOG-ACRIN STS the day of shipment. If the STS is unavailable, an Generic Specimen Submission Form (#2981) must be submitted with the karyotypes. Once STS is available, retroactively log the shipment into STS, using the actual collection and shipping dates.

Direct questions to [name] at [contact] or [contact].

The forms and karyotypes are to be shipped to:

[name]
Mayo Clinic Cytogenetic Laboratory
[name]
[name]
[name]
[contact]
[contact]

An STS shipping manifest form must be generated and shipped with all submissions.

Rev. 12/13

10.3 Epigenetics

E2906 incorporates a randomization to maintenance therapy with decitabine, a methyltransferase inhibitor, and affords a unique opportunity to study the epigenetic phenotype in AML at presentation and in remission. The following clinical & basic hypotheses will be studied in [name] laboratory at Weill Cornell Medical College, New York, NY.

Rev. 2/12

10.3.1 Clinical

Our preliminary data show that AML comes in different epigenetic subtypes, and that a phenotype of epigenetic instability seems to correlate with responsiveness with DNA methyltransferase inhibitors. In addition to the epigenetic unstable phenotype, many of the more defined AML epigenetic subtypes had different medical outcomes in retrospective studies and so may be highly clinically relevant. Interestingly, gene expression profiling failed to identify several of these subtypes alone, demonstrating the power of epigenetic analysis to capture important biological differences in AML. Finally, the integration of gene expression and epigenetic signatures were shown to synergistically capture biological differences between patients with leukemia.

Based on these data we predict that patients who present with AML and epigenetic instability will be the better candidates to respond to decitabine maintenance. Therefore we propose to perform expression and methylation profiling on all patients enrolled in 2906 and correlate their integrated epigenetic signatures with response to decitabine. Of equal importance we also predict that specific integrated epigenetic subtypes associated with differential clinical outcomes will be confirmed in this prospective study and could lead to an important advance in leukemia classification. The integrated signatures captured upon enrollment of these patients will be used to prospectively validate, confirm and possibly expand our ability to accurately segregate patients into biologically distinct cohorts. We plan to use these data to direct the design of future ECOG-ACRIN clinical trials.

10.3.2 Basic

Data from the published literature and our laboratory indicate that progressive alteration of epigenetic signatures in bone marrow cells occurs during normal aging. We hypothesize that certain epigenetic signatures associated with aging might constitute an epigenetic field defect that could result in leukemogenesis. We will examine the epigenetic profiles of remission marrow in patients randomized to observation vs decitabine in E2906 to determine whether epigenetic signature of apparently morphologically normal bone marrow is predictive of relapse or response to decitabine maintenance. Our data performed in fractionated vs unfractionated marrow from the same individuals indicate that epigenetic signatures indicative of aberrant epigenetic programming are equally readily evident in either case, and

are readily distinguishable between normal and abnormal samples. Therefore, we expect our experimental approach to successfully capture indications of epigenetic field defects in this patient cohort.

Rev. 2/12

10.4 Somatic Mutation Analysis

Following the model applied to E1900, a study in younger AML, E2906 will delineate the full spectrum of genetic lesions occurring in elderly patients with AML to discover potential differences dependent on age. The following clinical & basic hypotheses will be studied in [name] laboratory at Memorial Sloan Kettering Cancer Center, New York, NY.

10.4.1 Clinical

High throughput mutational profiling of patients enrolled in E1900 allowed us to delineate the somatic mutational frequencies of all known leukemia oncogenes and tumor suppressors in a large patient cohort who presented with de novo AML <60 years of age. Specifically, we found that mutations in ASXL1 and PHF6 are associated with an adverse outcome in the entire E1900 cohort and with primary induction failure. On the other hand, the IDH R140Q mutation was associated with an improved outcome in younger AML. In addition, we found that TET2, ASXL1, PHF6, DNMT3A, and WT1 mutations are associated with an adverse outcome in intermediate risk AML, including in patients without FLT3 mutations. Moreover, we found that patients with mutated DNMT3A, which occurs in 30% of younger AMLs, benefited from randomization to 90mg daunorubicin. By contrast, there was no benefit of higher dose chemotherapy for patients with wild-type DNMT3A, suggesting that DNMT3A mutations represent a novel biomarker with immediate therapeutic relevance. Analogous studies are currently underway to determine somatic genetic lesions in elderly AML from ECOG trial, E3999.

10.4.2 Methodology

Samples from E2906 will be analyzed as patients are accrued to the trial. High quality genomic DNA will be extracted from mononuclear cells provided by the LTSL, as done previously for E1900 and E3999 specimens. Control DNA will be isolated from normal T-cell contaminating the leukemia specimens or from remission samples. Genomic DNA from blasts and control cells will be subjected to Agilent SureSelect sequence capture followed by bar-coding and sequencing on our HiSeq2000. Genomic DNA will also be processed for reduced representation bisulfate sequencing and examined on the HiSeq2000. Excess DNA will be stored and made available to ECOG-ACRIN for distribution to other approved investigators. Validation will be done using amplicon based sequencing on our existing resequencing platform (used for E1900 and E3999 mutational studies) to facilitate higher throughput candidate gene mutational analysis of genomic DNA. Wherever possible, mutations will be analyzed in remission or T-cell DNA to ascertain whether specific alterations are somatic or in the germline. We will use our suite of computational biostatistical tools for identifying candidate somatic mutations. The data set will be evaluated for genetic signatures that distinguish

patient subtypes using unsupervised methods such as hierarchical clustering, principal component analysis, and consensus clustering. Signatures of co-occurring lesions will be determined using supervised methods including moderated T tests with correction for multiple testing, LEMMA, random forest, etc. The biological connectivity between gene sets and their genomic features will be derived using tools including iPAGE, FIRE, IPA, etc. We will use a series of statistical approaches to determine whether lesions in specific recurrently affected genes or pathways indicate risk of chemotherapy failure, disease recurrence or survival. In addition to univariate and multivariate analyses, we will use machine-learning algorithms like SuperPC and BDVAL to identify genetic, epigenetic, and integrated classifiers. All mutations detected will be validated by repeat PCR and sequencing on the unamplified diagnostic sample. Wherever possible, matched control DNA (remission or T-lymphocyte DNA) will be resequenced to determine if candidate disease alleles are somatic or present in germline.

Rev. 2/12 10.5 AML Prognostic Factors & Mechanisms of Resistance

Clofarabine (like cytarabine) requires active cellular uptake by equilibrative or concentrative nucleoside transporters, but is not a substrate for P-glycoprotein (Pgp). We hypothesize that the relative expression of Pgp will determine differential activity of clofarabine in subsets of patients who overexpress these transporters, and manifest in the CR rate. An aliquot of BM from pre-treatment will be evaluated for Pgp expression by flow cytometric assessment of the binding of antibody MRK-16⁸⁶, an antibody directed against a cell-surface epitope of Pgp. In addition, expression of CXCR4, which has been associated with inferior prognosis in retrospective studies in younger patients, will be assessed prospectively in this study by flow cytometry in the LTSL to correlate the intensity of its expression with other established prognostic factors (in particular with cytogenetics)⁸⁷.

Rev. 2/12

Rev. 12/13

Rev. 2/13

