1.6.4.2 Genetic Characterization of E2906 Leukemias

This study will perform a complete genetic characterization of patient leukemia cells using state of the art next

generation sequencing methods. The entire spectrum of somatic coding mutations will be identified, using Agilent Sure-Select exome capture followed by Illumina HiSeq2000 sequencing, the most powerful and economical approach for sequencing the coding sequence of genomes on a large scale. DNA from the patients' own T-lymphocytes or remission cells will be used as the matched germline control, using whole genome amplification to amplify small amounts of DNA that will be generated from these control cells, in order to distinguish true somatic variants. In addition, we will perform base-pair resolution DNA methylation sequencing across gene regulatory regions encompassing > four million individual cytosine residues. This will be achieved using an improved version of the reduced representation bisulfate sequencing protocol followed by Illumina HiSeq2000 sequencing. All mutations detected will be validated by repeat PCR and sequencing on the unamplified diagnostic sample. Wherever possible, matched control DNA (remission or T-lymphocyte DNA) will be resequenced to determine if candidate disease alleles are somatic or present in germline.

Rev. 2/13

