6.5.3 Flow Cytometry of BM Aspirate

Rev. 2/12 6.5.3.1 If one or more unique leukemia-associated immunophenotypes (LAIP) were identified at diagnosis, minimal residual disease (MRD) levels will be analyzed by multiparameter flow cytometry.

Rev. 2/12 6.5.3.2 Immunologic MRD must be below the level of detection (< 0.001) to qualify for "Leukemia-Free State".

Rev. 2/12 6.5.3.3 Any detectable immunologic MRD levels will be quantified and retrospectively correlated with relapse-free and overall survival.

6.5.4 Extramedullary leukemia must not be present.

6.5.5 If indeterminant, the BM Aspirate & biopsy should be repeated 1 week later.

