4. Peripheral blood and buccal swabs/rinse are to be submitted for banking per patient consent.

Rev. 12/13

Rev. 12/13

NOTE: It is required that biological sample submissions be logged into the ECOG-ACRIN Sample Tracking System (STS) (see Section [10.6](#)) for purposes of monitoring compliance.

Rev. 12/13		Pre-registratioin	Step 1 - Randomization (Baseline) ¹	Time of Outcome Following Induction (Prior to Consolidation) ⁸	End of Consolidation (Prior to 2 nd Randomization - Step 3) ⁴	Relapse	Send To
MANDATORY – Submissions required for central review							
	Karyotypes		X	X	X	X	Cyto lab ²
Rev. 2/13	Bone Marrow/ Peripheral Blood Smears (Wright-Giemsa stained)	X		X	X	X	
	Bone Marrow Aspirate (heparin, FIRST PULL) ^{6,9}	X		X	X	X	LTSL ³
	Peripheral Blood (heparin, green or EDTA purple top tubes, (4) 10 mL tubes, 30-40 mL) ⁶	X		X	X	X	
From patients who answer “YES” to “I agree to provide additional specimens for research.”							
	Peripheral Blood (red top tubes, (2) 10 mL tubes, 15-20 mL)		X	X	X	X	LTSL ³
	Buccal Rinse (preferred) or Swab ⁷		X				LTSL ³

Rev. 12/13

1. Pre-study bone marrow, peripheral blood, and smears must be submitted for centralized immunophenotyping to determine patient eligibility. This testing is mandatory for participation in this study.
2. Submit to the ECOG-ACRIN Cytogenetic laboratory at Mayo Clinic.
3. Submit to the ECOG-ACRIN Leukemia Translational Studies Laboratory (LTSL). Signed E2906 patient consents and HIPAA authorizations must be submitted to the LTSL prior to or at time of submission of pre-registration specimens to the LTSL.
4. At time of evaluation response.
5. [Deleted in Addendum #8]

Rev. 2/13, 8/13, 12/13

6. Bone marrow and peripheral blood will also be used for the optional correlative studies per patient consent.

Rev. 12/13

7. Buccal rinse (preferred) or swabs are strongly encouraged to be collected at baseline, but can be collected at any other time during the study, if necessary.

Rev. 12/13

8. At time of response assessment or off-study, whichever occurs first.

9. The laboratory will accept any amount as long as it represents a first pull. It is imperative that aspirate from a separate first pull be submitted. DO NOT SUBMIT THE SECOND OR THIRD PULL OF ASPIRATE FROM THE SAME ASPIRATION SITE.

8. Drug Formulation and Procurement

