- Submit from patients who answer "YES" to "*I agree to provide additional specimens for research.*"

NOTE: If samples designated for banking only are not submitted, please note the reason in the comments section of the Sample Tracking System.

Rev. 2/12

6. Buccal Cell Samples

Most commonly, institutions will have buccal swab kits for the collection of cells for HLA-typing. Alternatively, Scope, a commercial brand mouthwash, or normal saline in a small sealed bottle can be given to the patient for a mouthwash.

Aseptic techniques must be used to collect buccal cells from patients on-site and buccal cells must not be contaminated with cells from any other source. Patients should not brush their teeth or consume food prior to buccal cell collection.

If a cytobrush is used, the collection end should not be touched and the patient should not scrape his/her cheek too vigorously. The inside of the cheek should be scraped 6 times. Several models of cytobrushes are available, such as the Omni swab or Bio-Swab from Arrowhead Forensics or the Cyto-Pak CytoSoft Brush from Medical Packaging Corp.

- If mouthwash (e.g. Scope) or normal saline is used, the patient should pour approximately 10cc of mouthwash or saline into his/her mouth and

Rev. 12/13

vigorously swish it against the cheeks for 10 seconds and deliver the solution into a labeled 15cc polypropylene test tube or a sterile urine cup. Among mouthwashes, the Scope brand fares best in collecting buccal cells for the preparation of high-quality DNA in high yield.

Rev. 12/13

- It is important that buccal cells do not dry out during shipping. Institutions are advised to seal the container containing the buccal cells tightly. Ship containers on ice-packs, together with the patient's peripheral blood and bone marrow specimens.
- Submit from patients who answer "YES" to "*I agree to provide additional specimens for research.*"

NOTE: Buccal rinse (preferred) or swabs are strongly encouraged to be collected at baseline, but can be collected at any other time during the study if necessary.

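### The somatic mutation analysis allows a germline control (remission DNA) that only responders can supply, which can bias the mutation–chemoresistance association

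*Combined protocol and SAP*

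**What the plan says.** Two sections define the control. Section 1.6.4.2: "DNA from the patients' own T-lymphocytes or remission cells will be used as the matched germline control". Section 10.4.2: "Control DNA will be isolated from normal T-cell contaminating the leukemia specimens or from remission samples". The purpose is a two-way call. In 1.6.4.2, "matched control DNA (remission or T-lymphocyte DNA) will be resequenced to determine if candidate disease alleles are somatic or present in germline"; in 10.4.2, "Wherever possible, mutations will be analyzed in remission or T-cell DNA to ascertain whether specific alterations are somatic or in the germline". Neither section gives an order of priority, an allele-fraction threshold, or a rule for an allele still present in remission.

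The calls are then related to outcome. Section 10.4.2 asks "whether lesions in specific recurrently affected genes or pathways indicate risk of chemotherapy failure, disease recurrence or survival". Section 9.8 plans to assess known mutations against overall survival (OS) and response to therapy, and objective 2.2.8 covers the association between mutation and outcome.

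CR (Section 6.1) requires recovered counts, a marrow below 5% blasts by morphology, no Auer rods and no extramedullary disease. It has no molecular criterion. Section 3.2.6.5 admits patients whose AML followed MDS or a myeloproliferative disorder.

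A non-marrow tissue is also collected. Section 7.3: "Peripheral blood and buccal swabs/rinse are to be submitted for banking per patient consent". Section 10.1.2.1 adds a purity rule: "buccal cells must not be contaminated with cells from any other source". Section 10.4.2 does not name buccal DNA as a control.

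**The concern.** Whether a patient can have a remission control depends on the outcome under study. Non-responders can be controlled only with T-lymphocyte DNA; responders may be controlled with either source. If a clone survives into morphologic remission and its alleles are read as germline, true somatic calls disappear from responders and stay in non-responders. That is outcome-dependent misclassification. A mutation with no effect on response would look enriched among resistant patients.

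Neither safeguard in the plan reaches this. The multiplicity adjustment in 9.8 controls chance findings, not a systematic shift. Repeat sequencing of the diagnostic sample confirms calls that were kept but cannot restore one removed as germline. Without a record of the control used for each patient, a reader of the results could not tell whether it had happened.

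**Working it through.** **1. The plan's own figures.** Section 9.8 gives 81% power with 528 events (50% prevalence, hazard ratio 0.71) and with 501 events (20% prevalence, hazard ratio 0.65), Bonferroni-adjusted over about 20 mutations. The per-test level is 0.05/20 = 0.0025 two-sided, z = 3.023. Using power = Φ(√(D·p·(1−p))·|ln HR| − z):

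- √(528 × 0.25) × 0.3425 − 3.023 = 0.912, power 0.819
- √(501 × 0.16) × 0.4308 − 3.023 = 0.834, power 0.798

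Both reproduce to within about one point. They assume error-free mutation calls.

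**2. Inputs for the bias calculation.**

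- 635 patients with sequencing (9.8).
- CR rate 40% (9.4, stated for standard treatment and applied here to all): 254 responders and 381 non-responders.
- Prevalence p₀ = 30%, the figure in 10.4.1 for DNMT3A in younger AML.
- Loss m = (share of responders controlled with remission DNA) × (share of their mutated alleles that persist and are called germline). The documents give neither factor, so m is an assumption, shown at 5% to 30%. For example, 50% × 20% = 10% and 50% × 60% = 30%.
- No true association, and no loss of calls in non-responders.

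**3. Formulas.** The apparent prevalence in responders is p₁ = p₀(1 − m). The odds ratio (responders against non-responders) is [p₁/(1−p₁)]/[p₀/(1−p₀)]. The rejection rate comes from the two-proportion normal test, with pooled standard error under the null and unpooled under the alternative.

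**4. Worked case, m = 20%.** p₁ = 0.24 and the difference is 0.06. The pooled proportion is (254 × 0.24 + 381 × 0.30)/635 = 0.276, giving standard errors 0.0362 (pooled) and 0.0356 (unpooled). The odds ratio is (0.24/0.76)/(0.30/0.70) = 0.74. At 0.05: Φ[(0.06 − 1.96 × 0.0362)/0.0356] = Φ(−0.31) = 0.38. At 0.0025: Φ[(0.06 − 3.023 × 0.0362)/0.0356] = Φ(−1.39) = 0.08.

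**5. Results at 30% prevalence.**

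| Loss m | Prevalence in responders | Odds ratio | Rejection at 0.05 | Rejection at 0.0025 |
|---|---|---|---|---|
| 0 | 30% | 1.00 | 5% | 0.25% |
| 5% | 28.5% | 0.93 | 7% | 0.5% |
| 10% | 27% | 0.86 | 13% | 1% |
| 20% | 24% | 0.74 | 38% | 8% |
| 30% | 21% | 0.62 | 72% | 30% |

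At 0.0025 and m = 10%, 20%, 30%, the rates are about 4%, 29%, 76% at 50% prevalence and 0.8%, 4%, 13% at 20% prevalence. Section 9.8 states its multiplicity adjustment for the OS log-rank tests and gives no level for the response analyses, so both levels are shown.

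**6. Overall survival.** A 400-replicate simulation with no true effect assumed a hazard ratio of 0.3 to 0.5 for responders against non-responders. The spurious mutated/wild-type hazard ratio was about 1.03–1.04 at m = 10% and 1.07–1.17 at m = 30%.

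**The case against.** The case on the other side has real force.

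- **T cells are named too.** The same sentence offers T cells from the leukemia specimen, which non-responders can supply. A reader might infer that only responders have any germline control. The text does not say that; the restriction applies to the remission option alone, and where T cells are used there is no remission-related loss. This stands.
- **No subtraction rule is written.** A reader might infer that any allele seen in remission will be struck out as germline. The documents say only that control DNA is examined to decide the question, and they leave calling to unspecified computational tools. The risk is permitted, not prescribed. This stands.
- **Residual blasts alone would not look germline.** Below 5% blasts, a heterozygous blast mutation gives at most about 5%/2 = 2.5% of alleles, against about 50% for a heterozygous germline variant. Only a larger persisting non-blast clone could be confused with germline. This stands, and it is why antecedent MDS or a myeloproliferative disorder is the relevant example.
- **Sections 6.5 and 1.6.3.2 do not prove the point.** The statement "Any detectable immunologic MRD levels will be quantified and retrospectively correlated with relapse-free and overall survival" is conditional and concerns flow cytometry, and the Leukemia-Free State requires residual disease below detection. It does not show that the plan expects residual leukemia in remission marrow. Section 1.6.3.2 hypothesises epigenetic signatures, which say nothing about sequence variants.
- **The net direction is not certain.** T-cell DNA taken from a leukemia specimen may itself carry the clone. Calls lost that way in non-responders could offset the bias, and the documents cannot settle whether they would.
- **Germline samples are said to exist.** Section 1.6.5 says they are already being collected. That supports the feasibility of the change, but 10.4.2 still does not name buccal DNA.

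What remains is that nothing in the plan keeps the choice of control independent of response.

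**Conclusion.** The point holds as a permitted and avoidable bias, not a demonstrated one. The plan accepts a control that depends on outcome, sets no priority between sources, and has no rule for a persisting allele. The loss that arises through remission DNA can occur only in responders, so this component pushes the mutation–response association towards apparent resistance.

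Its size cannot be determined from the documents. It is negligible if remission DNA is rarely used or persistence is uncommon: at 5% loss and 30% prevalence, false rejection is about 7% at 0.05 and 0.5% at 0.0025. At 20% to 30% loss it is material for the response analysis, at about 38% to 72% at 0.05 and 8% to 30% at 0.0025. The OS effect is smaller. These figures rest on the assumed loss fraction, a 40% CR rate in all patients, no true association, and no call loss in non-responders. The plan's stated sample size, event counts and power do not change, and the primary comparison is untouched.

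**What to change.** In Sections 1.6.4.2 and 10.4.2:

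1. Choose the control by a rule that does not depend on response: T-lymphocyte DNA from the diagnostic sample, or the consented buccal sample already banked, with the same order of preference for responders and non-responders.
2. Do not call an allele germline from remission DNA alone. Report an allele present in remission but absent from the response-independent control as persistent somatic.
3. Record the control source for each patient, and repeat the mutation–response and mutation–survival analyses by control source.

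The cost is mainly laboratory-plan wording, one recorded field and a sensitivity analysis; no new sample type is needed. Buccal DNA depends on consent, so two sources would still be mixed, though no longer by outcome. Some T-cell DNA may be low-yield or not free of the clone. Section 10.4.2 has samples analysed as patients accrue, and Section 9.5 reports 727 accrued when Step 1 was suspended. Some may therefore already have been sequenced against remission DNA. Unless those controls are re-run at added cost, only the analysis by control source can address them.
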